	For unknown onset date of adverse events (or adverse drug reactions, etc.), the onset period will be calculated as 1 day. However, if the start month and date of Nesina treatment are same as the onset month and date of adverse events (or adverse drug reactions, etc.), the onset period will be calculated as the start date of Nesina treatment.
Mild type 2 diabetes mellitus	Patients who have type 2 diabetes mellitus with HbA1c (NGSP value) of \leq 7.4% at the start date of Nesina treatment
Patients with diabetic complication	Patients with any of the following complications: diabetic nephropathy, diabetic retinopathy, or diabetic neuropathy.
Patients with diabetic nephropathy	Patients with complication of PT Code 10012660 (diabetic end stage renal disease) or 10061835 (diabetic nephropathy).
Patients with diabetic retinopathy	Patients with complication of PT Code 10012688 (diabetic retinal oedema) or 10012689 (diabetic retinopathy).
Patients with diabetic neuropathy	Patients with complication of PT Code 10012645 (diabetic autonomic neuropathy), 10012676 (diabetic mononeuropathy), or 10012680 (diabetic neuropathy).
Patients with concurrent hypertension	Patients with concurrent disease of the Standardised MedDRA Query (hereinafter SMQ) Code 20000147 (hypertension (SMQ) narrow).
Patients with concurrent dyslipidemia	Patients with concurrent disease of the SMQ Code 20000026 (dyslipidaemia (SMQ) narrow).
Patients with concurrent hyperuricemia	Patients with concurrent disease of the PT code meeting the Takeda MedDRA Query 20.1 (hereinafter, TMQ 20.1) (blood uric acid increased).
Patients with concurrent liver disorder	Patients with concurrent disease of the SMQ Code 20000005 (hepatic disorders (narrow)).
Patients with concurrent hepatic steatosis	Patients with concurrent disease of the PT Code 10019708 (hepatic steatosis).
Patients with concurrent alcoholic hepatitis	Patients with concurrent disease of the PT Code 10019728 (hepatitis alcoholic).
Patients with concurrent chronic hepatitis	Patients with concurrent disease of the PT Code 10008909 (chronic hepatitis).
Patients with concurrent hepatic cirrhosis	Patients with concurrent disease of the PT Code 10019641 (hepatic cirrhosis).
Patients with concurrent renal disorder	Patients with concurrent disease of the TMQ 20.1 (renal disease).
Patients with concurrent nephrotic syndrome	Patients with concurrent disease of the PT Code 10029164 (nephrotic syndrome).
Patients with concurrent glomerulonephritis	Patients with concurrent disease of the PT Code 10018364 (glomerulonephritis) or the PT Code 10018367 (glomerulonephritis chronic).

Term	Definition
Patients with concurrent chronic renal failure	Patients with concurrent disease of the PT Code 10064848 (chronic kidney disease) or the PT Code 10038435 (renal failure).
Patients with concurrent heart disease	Patients with concurrent disease of the SOC Code 10007541 (cardiac disorders).
Patients with concurrent cardiac failure	Patients with concurrent disease of the SMQ Code 20000004 (cardiac failure (SMQ) narrow).
Patients with concurrent myocardial infarction	Patients with concurrent disease of the SMQ Code 20000047 (myocardial infarction (SMQ) narrow).
Patients with concurrent angina pectoris	Patients with concurrent disease of the SOC Code 10007541 (cardiac disorders) and the PT Code 10036759 (prinzmetal angina), PT Code 10002383 (angina pectoris), PT Code 10058144 (postinfarction angina), PT Code 10002388 (angina unstable), or LLT Code 10065566 (microvascular angina).
Patients with concurrent stroke-related disease	Patients with concurrent disease of cerebral infarction, cerebral haemorrhage, subarachnoid haemorrhage, or transient ischaemic attack, described below.
Patients with concurrent disease cerebral infarction	Patients with concurrent disease of the SOC Code 10029205 (nervous system disorders) and the PT Code 10006147 (brain stem infarction), PT Code 10008118 (cerebral infarction), PT Code 10008119 (cerebral infarction foetal), PT Code 10008034 (cerebellar infarction), PT Code 10019005 (haemorrhagic cerebral infarction), PT Code 10051078 (lacunar infarction), PT Code 10056237 (migrainous infarction), PT Code 10058571 (spinal cord infarction), PT Code 10060839 (embolic cerebral infarction), PT Code 10060840 (ischaemic cerebral infarction), PT Code 10064961 (thalamic infarction), PT Code 10067347 (thrombotic cerebral infarction), or PT Code 10069020 (basal ganglia infarction).
Patients with concurrent cerebral hemorrhage	Patients with concurrent disease of the SOC Code 10029205 (nervous system disorders) and the PT Code 10006145 (brain stem haemorrhage), PT Code 10008111 (cerebral haemorrhage), PT Code 10008112 (cerebral haemorrhage neonatal), PT Code 10008030 (cerebellar haemorrhage), PT Code 10018985 (haemorrhage intracranial), PT Code 10022840 (intraventricular haemorrhage), PT Code 10022841 (intraventricular haemorrhage neonatal), PT Code 10042365 (subdural haemorrhage neonatal), PT Code 10049236 (spinal epidural haemorrhage), PT Code 10048992 (spinal cord haemorrhage), PT Code 10050157 (cerebral haemorrhage foetal), PT Code 10052593 (meningorrhagia), PT Code 10058939 (thalamus haemorrhage), PT Code 10058940 (putamen haemorrhage), PT Code 10067057 (basal ganglia haemorrhage), PT Code 10067277 (cerebral microhaemorrhage), PT Code 10071205 (brain stem microhaemorrhage), PT Code 10071206 (cerebellar microhaemorrhage), PT Code 10072043 (central nervous system

Term	Definition
	haemorrhage), or PT Code 10073563 (Spinal subdural haemorrhage).
Patients with concurrent subarachnoid hemorrhage	Patients with concurrent disease of the PT Code 10042316 (subarachnoid haemorrhage), PT Code 10042317 (subarachnoid haemorrhage neonatal), PT Code 10073564 (spinal subarachnoid haemorrhage), LLT Code 10072201 (Asymptomatic subarachnoid haemorrhage).
Patients with concurrent transient ischemic attack	Patients with concurrent disease of the SOC Code 10029205 (nervous system disorders) and the PT Code 10044390 (transient ischaemic attack).
Patients with concurrent allergic disease	Patients with concurrent disease of bronchial asthma, pollinosis, allergic rhinitis, or allergic dermatitis, described below.
Patients with concurrent bronchial asthma	Patients with concurrent disease of the SOC Code 10038738 (respiratory, thoracic and mediastinal disorders) and the PT Code 10003553 (asthma), PT Code 10075084 (aspirin-exacerbated respiratory disease), PT Code 10003557 (asthma exercise induced), PT Code 10003559 (asthma late onset), PT Code 10041961 (status asthmaticus), PT Code 10001890 (alveolitis allergic), PT Code 10049585 (infantile asthma), PT Code 10070836 (occupational asthma), or PT Code 10064823 (asthmatic crisis).
Patients with concurrent pollinosis	Patients with concurrent disease of the PT Code 10048908 (seasonal allergy).
Patients with concurrent allergic rhinitis	Patients with concurrent disease of the PT Code 10039085 (rhinitis allergic).
Patients with concurrent allergic dermatitis	Patients with concurrent disease of the PT Code 10012434 (dermatitis allergic).
Patients with concurrent malignant tumor	Patients with concurrent disease of the SOC Code 10029104 (neoplasms benign, malignant and unspecified (incl cysts and polyps)).
Patients with concurrent malignant tumor (narrow sense)	Patients with concurrent disease of the SMQ Code 20000194 (malignant tumour (SMQ) narrow).
Patients with other concurrent disease	Patients with concurrent disease other than the above (diabetic complication, hypertension, dyslipidaemia, hyperuricaemia, liver disease, renal disease, heart disease, stroke-related disease, allergic disease, malignant tumor, or malignant tumor (narrow sense)).
Severity of renal impairment	Severity of renal impairment in the patient demographic section

Term	Definition
Age	If the start month and date of Nesina treatment is earlier than the birth month and date, calculate using the following formula: Start year of Nesina treatment – birth year – 1. If the birth month and date is earlier than or equal to the start month and date of Nesina treatment, calculate using the following formula: Start year of Nesina treatment – birth year. For unknown birth date, the birth date will be calculated as the 1st day of the birth month.
BMI	Calculate using the following formula: Weight (kg) / (0.0001 × Height (cm) × Height (cm)). Indicate to one decimal place rounded from two decimals.
Disease duration of type 2 diabetes mellitus (year)	Calculate using the following formula: (start date of Nesina treatment – diagnosis period of type 2 diabetes mellitus + 1) / 365.25. For unknown diagnosis month, calculate as January. Indicate to one decimal place rounded from two decimals.
Prior medication	Medications that patients were taking within 3 months before initiation of Nesina therapy.
Concomitant medication	Medications that patients were taking after the start date of Nesina treatment.
Start date of other diabetic drug and concomitant medication (other than diabetic drug)	Calculate as the start date of survey sheet (electronic).
End date of other diabetic drug and concomitant medication (other than diabetic drug)	Calculate as the end date of survey sheet (electronic).
Diabetic drugs	Drugs of the National Health Insurance (NHI) Drug List Code starting with 3969, 3961, 3962, 2492, 2499410, 2499411, 2499415, or 2499416.
α-glucosidase inhibitors	Drugs of the NHI Drug List Code starting with 3969003, 3969004, 3969009, or 3969102.
Thiazolidines	Drugs of the NHI Drug List Code starting with 3969005, 3969007, 3969100, 3969101, or 3969103.
Sulfonylureas	Drugs of the NHI Drug List Code starting with 3961 or 3969101.
Biguanides	Drugs of the NHI Drug List Code starting with 3962, 3969100, 3969104, or 3969105.
Rapid-acting insulin secretagogues	Drugs of the NHI Drug List Code starting with 3969006, 3969008, 3969013, or 3969102.
Insulin preparations	Drugs of the NHI Drug List Code starting with 2492.
DPP-4 inhibitors	Drugs of the NHI Drug List Code starting with 3969010, 3969011, 3969012, 3969014, 3969015, 3969016, 3969017, 3969024, 3969025, 3969103, 3969104, or 3969105.

Term	Definition
GLP-1 receptor agonists	Drugs of the NHI Drug List Code starting with 2499410, 2499411, 2499415, or 2499416.
SGLT2 inhibitors	Drugs of the NHI Drug List Code starting with 3969018, 3969019, 3969020, 3969021, 3969022, or 3969023.
Combination of diabetic drugs	Drugs of the NHI Drug List Code starting with 3969100, 3969101, 3969102, 3969103, 3969104, or 3969105.
Other diabetic drugs	Other diabetic drugs not classified into the above diabetic drug categories (α -glucosidase inhibitors, thiazolidines, sulfonylureas, biguanides, rapid-acting insulin secretagogues, insulin preparations, DPP-4 inhibitors, GLP-1 receptor agonists, SGLT2 inhibitors, or combination of diabetic drugs).
Hypertension drugs	
ARB Drugs of the NHI Drug List Code starting with the following 7 numbers: 2149039, 2149040, 2149041, 2149042, 2149044, 2149046, 2149048, 2149100, 2149110, 2149111, 2149112, 2149113, 2149114, 2149115, 2149116, 2149117, 2149118, 2149119, 2149120, 2149121, 2149122
 
Ca antagonists Drugs of the NHI Drug List Code starting with the following numbers: 2149019, 2149022, 2149027, 2149030, 2149034, 2149035, 2149037, 2149038, 2149043, 2149400, 2171006, 2171014, 2171019, 2171020, 2171021, 2171022, 2171405, 2190001, 2149114, 2149115, 2149116, 2149117, 2149118, 2149120, 2149121, 2149122, 2190101, 2190102, 2190103, 2190104
 
ACE inhibitors Drugs of the NHI Drug List Code starting with the following 4 numbers: 2144
 
Diuretics Drugs of the NHI Drug List Code starting with numbers 213 or the following 7 numbers: 2149003, 2149007, 2149012, 2149110, 2149111, 2149112, 2149113, 2149119, 2149122
 
α blockers Drugs of the NHI Drug List Code starting with the following numbers: 1234400, 214200210, 2149002, 2149015, 2149023, 2149026, 1152, 1149107, 1149114, 1149115, 2531001, 2149020
 
$\alpha\beta/\beta$ blockers Drugs of the NHI Drug List Code starting with the following numbers: 2149032, 2149018, 2123014, 2149009, 2123013, 2123003, 2149008, 2149016, 2442001, 2123011, 2149036, 2123016, 2149700, 2149031, 2149010, 2123001, 2123F01, 2149029, 2123008, 2149014, 2149021,

Term	Definition
	2149028, 2123015, 2123005, 2149025, 2123009, 2123403, 2149033, 2149011 Complication of hypertension drugs Drugs of the NHI Drug List Code starting with the following numbers: 2149110, 2149111, 2149112, 2149113, 2149114, 2149115, 2149116, 2149117, 2149118, 2149119, 2149120, 2149121, 2149122 Other Drugs of the NHI Drug List Code starting with the following numbers: 2149047, 2142004, 2149001, 2149017, 2145
Dyslipidaemia drugs	Statins Drugs of the NHI Drug List Code starting with the following numbers: 2189010, 2189011, 2189012, 2189013, 2189015, 2189016, 2189017, 2190101, 2190102, 2190103, 2190104 Fibrates Drugs of the NHI Drug List Code starting with the following numbers: 2183001, 2183002, 2183003, 2183004, 2183005, 2183006 EPA/DHA Drugs of the NHI Drug List Code starting with the following numbers: 2189019, 3399004 Other Drugs of the NHI Drug List Code starting with the following numbers: Dugs, other than the above, of the NHI Drug List Code starting with 218, 2900002, or 3133001.
Concomitant medication (other)	Drugs other than the above (diabetic drugs, hypertension drugs, or dyslipidaemia drugs).
Protease Inhibitor	Use the results of the drug name in the survey sheet (electronic) coded with the NHI Drug List (Appendix 1. List of Protease Inhibitors).
Renal excretory drugs	Use the results of the drug name in the survey sheet (electronic) coded with the NHI Drug List (Appendix 2. List of Renal Excretory Drugs).
Nesina treatment period (days)	Actual treatment period from the start date to the end date of Nesina treatment. However, the washout period is excluded from the treatment period. Calculate using the following formula: End of Nesina treatment – start date of Nesina treatment + 1 (grand total). (Consider the washout period.)
Mean daily dose of Nesina	Calculate using the following formula: Total of “daily dose of Nesina × Nesina treatment period at the relevant dose” / Nesina treatment period. For the calculation of Nesina treatment period, refer to the above. If the daily dose of Nesina is a number outside specification in the survey sheet (electronic) and is actual number, use the relevant number.

Term	Definition
HbA1c (NGSP value)	
The NGSP value only will be used in this analysis.
 
For the HbA1c (JDS value), calculate using the following formula: $\text{NGSP value (\%)} = 1.02 \times \text{JDS value (\%)} + 0.25\%$ 
 
The HbA1c (international standard value) will be handled as the NGSP value.

Change in HbA1c	
For HbA1c converted to the NGSP value, calculate using the following formula: Laboratory value – Laboratory value at the start of Nesina treatment.

Glycemic control achievement rate	
Divide the following two categories for the Glycemic control achievement rate:
 
HbA1c (NGSP converted value) [Unit %] NGSP (%): < 6.0, ≥6.0 / < 7.0, ≥ 7.0

non-HDL cholesterol	
Calculate using the following formula: “Total cholesterol” – “HDL cholesterol.”

Summary statistics	
Number of patients, mean, standard deviation, minimum, first quartile, median, third quartile, and maximum.

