1.3 Display digit

Term	Definition
Percentage (%)	
Percent of patients with adverse events or adverse drug reactions, etc. or percent of adverse events or adverse drug reactions, etc. :
 
Indicate to two decimal places rounded from three decimals.
 
Other than the above:
 
Indicate to one decimal place rounded from two decimals.

Summary statistics	
Mean, median, first quartile, and third quartile:
 
Indicate one lower digit rounded from two lower digits than the digit of the to-be evaluated data.
 
Standard deviation:
 
Indicate two lower digits rounded from three lower digits of the to-be evaluated data.
 
Minimum and maximum
 
Indicate the same digit number as that of the to-be evaluated data (refer to Section 1.6).

p-value	Indicate to three decimal places rounded down from four decimals.

Term	Definition
	If the data is rounded down from four decimal places and less than 0.001, display as $p < 0.001$.

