1.6 Display Data Digit

Display digits are described as below.

Term	Display digit	Unit
HbA1c	0.1	%
Fasting blood glucose level	1	mg/dL
Fasting insulin level	0.1	μU/mL
Fasting triglyceride	1	mg/dL
Total cholesterol	1	mg/dL
HDL-cholesterol	1	mg/dL
LDL-cholesterol	1	mg/dL
Non-HDL cholesterol	1	mg/dL
Systolic blood pressure	1	mmHg
Diastolic blood pressure	1	mmHg
Weight	0.1	kg
BMI	0.1	kg/m ²
Age	1	Year
Disease duration of type 2 diabetes mellitus	0.1	Year
Height	1	cm
Week of pregnancy	1	Week
Nesina treatment period	1	Day
Mean daily dose of Nesina	0.01	mg

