6.0 Efficacy Tabulation and Analysis

6.1 Changes in HbA1c

(1) Patients to be tabulated and analyzed

Efficacy Analysis Set

(2) Details of tabulation and analysis

For HbA1c (NGSP values), summary statistics will be calculated at each testing time point (start of Nesina treatment, 3 months, 6 months, 12 months, 18 months, 24 months, 30 months, and 36 months after Nesina treatment and last evaluation). For changes, summary statistics and the mean 95% confidence intervals will be calculated and the paired t-test will be performed.

Measured values of HbA1c (NGSP values) will be plotted and for the changes a bar graph will be created excluding the unknown category at each testing time point (start of Nesina treatment, 3 months, 6 months, 12 months, 18 months, 24 months, 30 months, and 36 months after Nesina treatment and last evaluation).

(3) Number of tables and figures

Table 6.1-1 and Figure 6.1-1

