6.2 Glycemic control achievement rate (HbA1c)

(1) Patients to be tabulated and analyzed

Efficacy Analysis Set

(2) Details of tabulation and analysis

The Glycemic control achievement rate for HbA1c (NGSP value) will be tabulated ($< 7.0\%$, $\geq 7.0\%$ / $< 6.0\%$, $\geq 6.0\%$) and a bar graph will be created ($< 7.0\%$, $\geq 7.0\%$ / $< 6.0\%$, $\geq 6.0\%$) at each testing time point (start of Nesina treatment, 3 months, 6 months, 12 months, 18 months, 24 months, 30 months, and 36 months after Nesina treatment and last evaluation) (the unknown category will be excluded for the bar graph).

(3) Number of tables and figures

Table 6.2-1 and Figure 6.2-1

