6.4 Changes in HbA1c, etc. by Factor Probably Affecting Efficacy

(1) Patients to be tabulated and analyzed

Efficacy Analysis Set

(2) Details of tabulation and analysis

For changes in HbA1c (NGSP values), summary statistics and the mean 95% confidence intervals will be calculated and the paired t-test will be performed at each testing time point (start of Nesina treatment, 3 months, 6 months, 12 months, 24 months, and 36 months after Nesina treatment and last evaluation).

The Glycemic control achievement rate for HbA1c ($< 7.0\%$, $\geq 7.0\%$ / $< 6.0\%$, $\geq 6.0\%$) at each testing time point (start of Nesina treatment, 3 months, 6 months, 12 months, 24 months, and 36 months after Nesina treatment and last evaluation) will be tabulated at the following parameters:

i Sex (Male, Female)

ii Age (< 65 years, ≥ 65 years)

iii Age (< 75 years, ≥ 75 years)

iv Concurrent renal disorder (No, Yes)

v HbA1c (NGSP value) at the start of Nesina treatment ($< 6.0\%$, 6.0% to $< 7.0\%$, 7.0% to $< 8.0\%$, $\geq 8.0\%$)

vi Mean daily dose of Nesina (> 25 mg, 25 to > 12.5 mg, 12.5 to > 6.25 mg, or 6.25 mg)

vii Concomitant diabetic drugs (α -glucosidase inhibitors, thiazolidines, sulfonylureas, biguanides, rapid-acting insulin secretagogues, or insulin preparations)

(3) Number of tables and figures

Tables 6.4-1 to 6.4-14

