6.5 Changes in HbA1c, etc. in Patients with Special Demographics

(1) Patients to be tabulated and analyzed

Efficacy Analysis Set.

However, patients will be evaluated for Parameter (ii) in (2) Details of tabulation and analysis.

Patients with moderate or higher renal impairment in the Efficacy Analysis Set.

(2) Details of tabulation and analysis

For changes in HbA1c (NGSP values), summary statistics and the mean 95% confidence intervals will be calculated and the paired t-test will be performed at each testing time point (start of Nesina treatment, 3 months, 6 months, 12 months, 24 months, and 36 months after

Nesina treatment and last evaluation).

The Glycemic control achievement rate for HbA1c ($< 7.0\%$, $\geq 7.0\%$ / $< 6.0\%$, $\geq 6.0\%$) at each testing time point (start of Nesina treatment, 3 months, 6 months, 12 months, 24 months, and 36 months after Nesina treatment and last evaluation) will be tabulated at the following parameters:

- i. Severity of renal impairment (Normal + Mild, Moderate + Severe)
- ii. Mean daily dose of Nesina (> 25 mg, 25 to > 12.5 mg, 12.5 to > 6.25 mg, or 6.25 mg)

(3) Number of tables and figures

Tables 6.5-1 to 6.5-4

Statistical Analysis Plan

Nesina Tablets Special Drug Use Surveillance: Mild Type 2 Diabetes Mellitus

(Final Analysis)

Takeda Pharmaceutical Company Limited.

PPD

A rectangular area of the document is redacted with a solid blue color.

PPD

A large rectangular area of the document is redacted with a solid blue color.

Version 2.0, Created on January 30, 2018

Table of Contents

1.0	Definition of Terms and Handling of Laboratory/Measured Data.....	1
1.1	Definitions	1
1.2	Important Identified Risks, Potential Risks, and Missing Information.....	10
1.3	Display digit.....	11
1.4	Level of Significance and Confidence Coefficient.....	12
1.5	Handling of Laboratory/Measured Data	12
1.6	Display Data Digit.....	12
2.0	Disposition of Patients (Patient Diagram).....	14
3.0	Patient Demographics	15
4.0	Details of Treatment.....	18
4.1	Initial Dose of Nesina and Mean Daily Dose of Nesina, by Severity of Renal Impairment.....	19
5.0	Safety Tabulation and Analysis	21
5.1	Occurrence of adverse events and adverse drug reactions / infections.....	21
5.1.1	Occurrence of adverse events.....	21
5.1.2	Occurrence of adverse drug reactions / infections.....	21
5.1.3	Important Identified Risks, Important Potential Risks, and Important Missing Information....	22

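### Does the SAP need a rounding rule for converted HbA1c before the 6.0% and 7.0% cuts are applied?

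*SAP*

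**What the plan says.** SAP 1.1 analyses NGSP values only. JDS entries are converted ("For the HbA1c (JDS value), calculate using the following formula", namely 1.02 × JDS + 0.25), and international standard values are used as NGSP unchanged. The achievement entry in the same section splits the converted value at 6.0 and 7.0, with strict inequality on the lower side. Neither entry has a rounding step, although BMI and disease duration in that section each carry one.

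The only precision given for HbA1c is 0.1, in SAP 1.6 ("Display digits are described as below"). SAP 1.3 points there when it sets the digit for minimum and maximum: "Indicate the same digit number as that of the to-be evaluated data (refer to Section 1.6".

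The cuts are used in SAP 6.2 ("The Glycemic control achievement rate for HbA1c (NGSP value) will be tabulated"), in 6.4 and 6.5, and in the baseline classes of 3.0 and 6.4(v) ("HbA1c (NGSP value) at the start of Nesina treatment"). Protocol 9.1 records registration HbA1c in JDS. Protocol 9.4 accepts JDS, international standard or NGSP at the visits; one protocol version lists only the first two.

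**The concern.** Only JDS entries pass through the formula, so only they acquire extra decimals. Two patients with the same HbA1c could be classed differently because one laboratory reported JDS 6.6 and another NGSP 7.0, although both would display as 7.0 at the digit in SAP 1.6. A patient whose site changed scale during follow-up could move from achieved to not achieved with no real change. Two programmers could also produce different tables from the same SAP. At stake would be the comparability of the achievement rates across units and time points, and which patients fall in each baseline stratum. The cure looks almost free: one line and one recode.

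**Working it through.** **Inputs.** Conversion and cuts: SAP 1.1. Display digit 0.1: SAP 1.6. Entry limit JDS ≤ 7.0%: Protocol 4.1. Mild limit NGSP ≤ 7.4%: SAP 1.1.

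**Reproducing the plan's own figure.** 1.02 × 7.0 + 0.25 = 7.390, which becomes the SAP's 7.4 after rounding to 0.1. The sponsor therefore appears to have worked to one decimal when carrying the entry limit over to NGSP.

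**Which readings are affected.** All one-decimal JDS values from 3.0 to 15.0 were converted and classed with and without rounding to 0.1. The readings near the cuts are:

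| JDS | Converted | Rounded | Class changes? |
|---|---|---|---|
| 5.5 | 5.860 | 5.9 | no |
| 5.6 | 5.962 | 6.0 | yes, at < 6.0 |
| 5.7 | 6.064 | 6.1 | no |
| 6.5 | 6.880 | 6.9 | no |
| 6.6 | 6.982 | 7.0 | yes, at < 7.0 |
| 6.7 | 7.084 | 7.1 | no |
| 7.0 | 7.390 | 7.4 | no, at ≤ 7.4 |
| 7.1 | 7.492 | 7.5 | no, at ≤ 7.4 |
| 7.5 | 7.900 | 7.9 | no, at < 8.0 |
| 7.6 | 8.002 | 8.0 | no, at < 8.0 |

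Only 5.6 and 6.6 change side anywhere in the scan.

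**What rounding gains and costs.** Assume each laboratory rounds half-up to 0.1 on its own scale and the linear formula is exact. Then < 7.0 means a true NGSP value below 6.95 for a reported NGSP value. For a JDS entry it means below 1.02 × 6.65 + 0.25 = 7.033 without rounding, and below 1.02 × 6.55 + 0.25 = 6.931 with it. At 6.0 the three limits are 5.95, 1.02 × 5.65 + 0.25 = 6.013 and 1.02 × 5.55 + 0.25 = 5.911.

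| Cut | JDS handling | Gap to reported NGSP | Distance from nominal cut |
|---|---|---|---|
| 7.0 | unrounded | 7.033 − 6.95 = +0.083 | 7.033 − 7.0 = 0.033 |
| 7.0 | rounded | 6.931 − 6.95 = −0.019 | 7.0 − 6.931 = 0.069 |
| 6.0 | unrounded | 6.013 − 5.95 = +0.063 | 6.013 − 6.0 = 0.013 |
| 6.0 | rounded | 5.911 − 5.95 = −0.039 | 6.0 − 5.911 = 0.089 |

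If true values are spread evenly within a reading, the share of JDS 6.6 readings truly below 7.0 is ((7.0 − 0.25)/1.02 − 6.55)/0.10 = 68%. For JDS 5.6 and 6.0 it is ((6.0 − 0.25)/1.02 − 5.55)/0.10 = 87%. Rounding would class all of them as not achieved.

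**Size in percentage points.** The change in a rate from choosing to round is (JDS share of entries) × (share of JDS entries reading 6.6, or 5.6). The documents give neither factor. Assuming a JDS share of 10% to 100% and normal JDS values with mean 5.9 to 6.7 and SD 0.3 to 0.6, truncated at 7.05, the change runs from about 0.1 to 14 points at 7.0 and from 0 to 8 at 6.0. That range is too wide to rank the point. Its top end needs every entry to be JDS, and then no difference between units exists. The truncation also fits baseline only, whereas most of the rates are post-baseline.

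**The case for a change.** The strongest case for acting is that the ambiguity is real and costs one sentence to remove. SAP 1.1 writes a rounding step for BMI and disease duration but not for HbA1c, and the 0.1 in SAP 1.6 is labelled a display digit, so a literal programmer would class 6.982 as below 7.0. Both affected readings lie inside the enrolled range. The cuts feed every achievement table, and SAP 6.4 runs paired t-tests within baseline strata whose membership can move. If the JDS share falls during follow-up, the effect could differ between baseline and 36 months.

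The arithmetic and the gap in wording stand. So does the effect on the composition of the strata, though it concerns one reading at each boundary. What does not follow is that one convention is right. A calculated 6.982 is below 7.0, and classing it so is legitimate. Rounding buys agreement between units, incompletely, at the price of moving further from the stated cut.

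Three side issues add nothing. The ≥ 8.0% class in 6.4(v) must be empty, because the Efficacy Analysis Set stops at 7.4%; an empty row is harmless, and the same classes serve 3.0, where non-mild patients are included. Separate cuts for sulfonylurea users would be a preference that no SAP objective asks for. The pair of 7.4% classes in 3.0, printed with ≥ and >, is a clerical slip that the definition of mild disease already resolves.

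**Conclusion.** No change follows. The classing digit is unstated, but analysts can fill the gap sensibly: 0.1 is the HbA1c digit in SAP 1.6 and is what turns 7.39 into the 7.4 mild limit ("Patients who have type 2 diabetes mellitus with HbA1c (NGSP value) of" at most 7.4%). An analyst who kept the unrounded value would also have a defensible table.

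The reach is narrow: two JDS readings, in rates that SAP 6.2 tabulates and plots without a test, confidence interval or target, and in membership of the baseline strata. The overall analysis in SAP 6.1 ("For changes, summary statistics and the mean 95% confidence intervals will be calculated and the paired t-test will be performed") uses no cut. The mild definition and the Efficacy Analysis Set give the same answer either way.

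The list of affected readings is exact for one-decimal JDS values. The gap figures rest on half-up laboratory rounding to 0.1 and an error-free conversion, and the 68% and 87% also on an even spread within each reading. The effect on any reported rate remains unknown without the unit mix and the HbA1c distribution.
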